6. TREATMENT PROCEDURES AND OBSERVATIONS

6.1. SAFETY EVALUATION

Safety will be evaluated through adverse event monitoring, clinical evaluations (i.e., vital signs, physical examinations), laboratory tests (i.e., hematology, serum chemistries, and urinalysis), lung injury severity (Murray lung injury score), oxygenation (PaO2/FiO2 ratio and oxygenation index), and microbiology (i.e. sputum cultures), chest imaging (i.e. chest CT) from the signing of informed consent and throughout the patient's participation in this treatment protocol.

6.1.1. LABORATORY AND CLINICAL EVALUATIONS

- Baseline is at enrollment (within 3 days- excluding COVID-19 PCR test which can obtained within 90 days to avoid repeat testing). Days post infusion are calculated from the first infusion. The "*" signifies that the test results from standard of care testing will be used however, they do not need to be obtained specifically for the study
- Height and weight with baseline physical examination
- Hematology: hemoglobin, hematocrit, platelet count, white blood cell (WBC) count, and WBC differential at baseline, day of infusion, Day 4, Day 7*, and Day 28*
- Coagulation: prothrombin time (PT)/aPTT/INR, D-dimer at baseline, Day 4*, and Day 28*
- Serum chemistry: CRP, ESR, AST, ALT, LDH, total bilirubin, alkaline phosphatase, total protein, albumin, sodium, potassium, chloride, carbon dioxide, calcium, blood urea nitrogen (BUN), creatinine, creatinine clearance and glucose at baseline, day of infusion*, Day 4*, Day 7*, and Day 28*
- Urinalysis*: pH, specific gravity, protein, glucose, ketones, blood, leukocyte esterase, and nitrite at baseline. Microscopy required only to follow-up clinically significant abnormal findings
- Chest x-ray* at baseline, Day 4*, Day 7*, and Day 28*
- ABGs prior, 1-4 hours after, Day 4*, Day 7*, and Day 28*
- COVID-19 PCR at baseline (do not repeat testing if obtained within 90 days of enrollment), day
 4*, 7*, and 28* post treatment
- Donor referral panel at baseline
- HLA typing (high resolution class I and class II) at baseline
- PRA (Anti-HLA antibodies) at baseline and day 28
- PaO2/FiO2 and oxygenation index endpoints (based on invasive or non-invasive mechanical ventilation or high flow nasal cannula use). To be done at Baseline, Day 1, Day 2, Day 4, and if on continued ventilation Day 7, and Day 14. PaO2/FiO2 may be calculated from an arterial blood gas or imputed from the SpO2/FiO2 table (Brown, et al. Chest 2016)
- Day 28 mortality
- Hospital discharge
- Invasive or non-invasive mechanical ventilation-free days and oxygen-free days
- Lung injury severity score (Murray) at Baseline, Day 1, Day 2, Day 4, Day 7, and Day 14. The
 most recent chest x-ray will be used to calculate the Murray score. For patients on pressure
 support mode ventilation, the peak pressure will be used in place of the plateau pressure to
 calculate compliance
- Any laboratory or imaging can be repeated outside the protocol requirements at the discretion of the treating physicians

Confidential Page **20** of **32**

Please see table of events for details and time windows for each of the tests. In addition, clinical data will be collected on other interventions that would be expected to affect oxygenation:

- a. Use and duration of prone ventilation
- b. Use and duration of neuromuscular blocker administration
- c. Use and duration of inhaled nitric oxide
- d. Use and duration of inhaled epoprostenol
- e. Use and duration of corticosteroids (methylprednisolone, prednisone, hydrocortisone, dexamethasone

The treating physician will review all clinical laboratory results, and clinically significant findings will be reported as AEs and followed or treated according to institutional guidelines or the treating physician's medical judgment.

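### Routine hematology and chemistry are optional at Day 28, so the results will probably over-represent the sickest survivors, although the blood draw needed to make them complete is already required

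*Combined protocol and SAP*

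**What the plan says.** Section 6.1 lists "laboratory tests (i.e., hematology, serum chemistries, and urinalysis" among the means of evaluating safety. Section 6.1.1 then sets the schedule and uses a star for tests where "test results from standard of care testing will be used however, they do not need to be obtained specifically for the study". Each of the following extracts ends just before a star on Day 28, except the PCR extract, which shows its star.

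- Hematology: "WBC differential at baseline, day of infusion, Day 4, Day 7*, and Day 28". It is a study test through Day 4 and starred at Days 7 and 28. (The section 7 table, as it reads in the text available, has no infusion-day mark for hematology.)
- Serum chemistry: "creatinine clearance and glucose at baseline, day of infusion*, Day 4*, Day 7*, and Day 28". Only the baseline panel is a study test.
- Coagulation: "D-dimer at baseline, Day 4*, and Day 28". It is starred at Days 4 and 28.
- COVID-19 PCR: "4*, 7*, and 28* post treatment". It is starred at every post-infusion time.
- PRA: "PRA (Anti-HLA antibodies) at baseline and day 28". It has no star.

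The section 7 table carries the same stars. Section 6.1.2 plans a Day 28 follow-up visit and does not limit it to inpatients. Section 6.1.1 also says of laboratory results that "clinically significant findings will be reported as AEs". The adverse-event row in section 7, as it reads in the text available, marks infusion days, Day 4, Day 7 and Day 90 (serious events only), but not Day 28. Section 8.3 has daily follow-up in hospital and for 7 days after infusion. Section 9.4 summarizes other outcomes descriptively and has no rule for missing laboratory values.

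**The concern.** A test that is done only when a clinician orders it is done more often in patients who are still ill. By Day 28 the patients divide into those who have died, those who have gone home and those still under care. Only the last group can be relied on to have routine hematology and chemistry. Day 28 summaries would then describe the sicker survivors, and a change from Day 4 to Day 28 would mix a change in patients with a change in who was tested.

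The same mechanism touches adverse events. A liver, kidney or blood-count abnormality is recorded under 6.1.1 only if the test was done, so discharged patients may be under-ascertained. If one arm recovers faster, the shortfall would also differ between arms.

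**Working it through.** The plan states no figure on this point, so there is nothing to reproduce. The first step is a reading of the schedule and the second an illustration of size.

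**Schedule at Day 28.** Hematology, chemistry, coagulation and PCR are optional. PRA is required. A visit is planned for all patients, and footnote n of section 7 names Day 28 as the time the primary endpoint is evaluated. Blood is therefore due from every survivor at that visit, but no routine safety panel is.

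**Inputs for size.** 20 patients per arm, 30% placebo recovery by Day 28 and an illustrative hazard ratio (HR) of 2.0, all from section 9.1.2. Mortality to Day 28 is an assumption. The synopsis gives 30-60% for ARDS, and section 3.6 reports Phase 1 deaths on Days 7 and 27, which is 2 of 10 by Day 28. The range shown is 20-60%.

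**Formulas.**
- Recovered on hCT-MSC = 1 - 0.70^2 = 0.51, or 10.2 of 20. On placebo it is 6.0 of 20.
- Not recovered: 14.0 on placebo, 9.8 on hCT-MSC.
- Alive and unrecovered with equal mortality m: 20 x (1 - recovered - m).
- Alive and unrecovered on hCT-MSC if deaths are in proportion to non-recovery: 9.8 x (1 - m/0.70).

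| Mortality m | Placebo survivors | Placebo, alive and unrecovered | hCT-MSC, equal mortality | hCT-MSC, proportional mortality |
|---|---|---|---|---|
| 20% | 16 | 10.0 | 5.8 | 7.0 |
| 30% | 14 | 8.0 | 3.8 | 5.6 |
| 40% | 12 | 6.0 | 1.8 | 4.2 |
| 60% | 8 | 2.0 | 0 (formula gives -2.2) | 1.4 |

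**With no treatment effect** (HR 1.0, equal mortality), both arms follow the placebo columns. The unrecovered are then 10/16 = 63%, 8/14 = 57%, 6/12 = 50% or 2/8 = 25% of survivors. If results come mainly from these patients, the remaining survivors are largely absent from the Day 28 summaries in both arms.

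**Early time points.** Under a constant hazard, the expected number recovered is:
- Day 4: 20 x (1 - 0.70^(4/28)) = 1.0 on placebo and 20 x (1 - 0.70^(8/28)) = 1.9 on hCT-MSC.
- Day 7: 20 x (1 - 0.70^(7/28)) = 1.7 on placebo and 20 x (1 - 0.70^(14/28)) = 3.3 on hCT-MSC.

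Patients enter on ventilatory support or high-flow oxygen (4.1) and have ICU monitoring (4). Day 4 and Day 7 chemistry is therefore probably near complete although starred. The problem is concentrated at Day 28.

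**The case against.** Using standard-care results is an open design choice in a small descriptive pilot. Section 3.3 measures primary safety by infusion reactions, later reactions attributed to the product, and new antibodies. The only laboratory item among these, PRA, is required at Day 28. Section 9.4 names no comparison of laboratory values or laboratory adverse events between arms. All of this stands, and it confines the point to supportive data. A late laboratory abnormality could lead someone to recognize a product reaction, but the plan does not define that component through these tests, and the effect cannot be sized.

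A reader might infer that Day 28 values will come only from inpatients. The documents do not say so: the Day 28 visit is open to all, and outpatient standard-care results would count. The visit does not close the gap, however, because the star removes any duty to test there.

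A reader might also infer that the arms will be tested unequally, so that hCT-MSC would look safer on laboratory events or worse on Day 28 means. That requires a treatment effect. The HR of 2.0 is a power illustration, not an expectation, and with HR 1.0 and equal mortality the expected counts are equal. Being alive and unrecovered is also only a proxy for being under care, since the plan's recovery definition includes some patients still in hospital. The equal-mortality formula turns negative on hCT-MSC at 60%, inside the synopsis range, so the counts show direction and rough size only.

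**Conclusion.** The point holds for hematology and serum chemistry at Day 28. Both are named means of evaluating safety and both are optional at that visit, so availability will probably depend on whether a survivor is still under care. That over-represents the sickest survivors in both arms whether or not the product works, and it may under-ascertain laboratory-detected adverse events after discharge.

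A difference between arms is conditional on faster recovery with hCT-MSC. At HR 2.0 and an assumed 30% mortality, about 8 of 20 placebo patients would be alive and unrecovered. On hCT-MSC the figure is about 4 of 20 with equal mortality, or 5.6 of 20 if deaths are in proportion to non-recovery.

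The documents do not support a claim that the named primary endpoint components are biased, or that all safety laboratories are affected. The change is worth making because the remedy is cheap and the visit and blood draw already exist.

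**What to change.** 1. In 6.1.1 and section 7, remove the star from Day 28 hematology and serum chemistry, and run both on the blood already drawn for the Day 28 PRA.
2. In section 7, mark adverse-event assessment at Day 28, and align 8.3 with it, so that clinically significant results are recorded as 6.1.1 intends. Without this, removing the star would yield values with no scheduled step to record them as events.
3. In 9.4, state that results still starred are reported with the number tested per arm. This covers coagulation and PCR, and Day 4 and Day 7 chemistry. Keep the Day 4 and Day 7 chemistry summaries by arm, because those data are probably near complete and lie closest to infusion.

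The cost is two routine panels in patients already discharged, plus the wording. In the illustration with equal 30% mortality, and treating recovered patients as discharged, that is (14 - 8.0) + (14 - 3.8) = about 16 patients across both arms. No extra visit or blood draw is added.

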6.1.2. OTHER SAFETY CONSIDERATIONS

Physical examinations (by PI, sub-I or clinical team) will be performed at baseline, following IV infusion (as clinically indicated by the clinical team), and daily during hospitalization. Patient will have a follow-up visit at Day 28 (+/-2 days) and 90 days after Day 1 of investigational product administration. Data analysis will commence at 28 days. Follow up at 90 days will be to assess for any delayed SAEs. Please see table of events for details. The baseline and end of treatment (or termination) examination will be a complete physical examination; other examinations should be focused, at the discretion of the treating physician, to assess changes from the previous examination.

Other safety assessments will include vital signs and oxygen requirement. The treating physician will review all vital sign results and oxygenation parameters, and clinically significant findings will be reported as AEs and followed or treated according to institutional guidelines or the treating physician's medical judgment.

Any immediate hypersensitivity reaction after infusion will result in discontinuation of treatment.

Confidential Page **21** of **32**

7 TREATMENT VISIT SCHEDULE

Evaluation	Baseline (within 3 days)	Infusion Days ⁱ	Day 4	Day 7 (+ 1 day)	Day 14 (+ 2 days)	Day 28 (+2 days) -	Day 90 (+ 5 days)
Informed Consent	Х						
Medical History, height, weight, and Demographics	х						
Physical Exam	Х	Xj	Х	Х			
Vital Signs ^a	Χ	X ^{bj}					
Hematology ^c	Х		Х	X*		X*	
Serum Chemistry d	Х	X*	Χ*	X*		X*	
Coagulation ^e	Х		X*			X*	
Pregnancy Test ^f	Х						
EKG	X*						
Urinalysis	X*						
HLA Typing	Х						
PRA	Х					Х	
Donor screening panel	Х						
COVID PCR	Х		Χ*	X*		X*	
Chest x-ray	Х*		Χ*	X*		X*	
ABG	Х	Xgj	Χ*	X*		X*	
Pre-medications		Χj					
Concomitant Meds	X	X	Х	X		Х	
Adverse Events Assessment		X	Х	X			Х
Lung Injury Severity Score (Murray)	х	Xı	Х	Х	X	Х	

LAR

Confidential Page 22 of 33

hCT-MSC Infusion		Xh					
PaO2/FiO2	Х	Xj	Х	Х	X		
Prone Ventilation ^k	Х	Х	X	Х			
Neuromuscular				X			
blocker ^k	X	X	X				
Inhaled nitric acid ^k	Х	Х	X	Х			
Inhaled				X			
epoprostenaol ^k	X	X	X				
Corticosteroids ^k	X	X	X	X			
Survival						X	Х
Oxygen use							X ^m

- a. Blood Pressure, Heart Rate, Respiratory Rate, Temperature, and O₂ Saturation
- b. Vitals are taken prior to pre-medications, prior to infusion, every 15 minutes during infusion, every 30 minutes post infusion X 2, then hourly X 4.
- c. Hematology: Hemoglobin, Hematocrit, platelet count, White Blood Cells, and differential
- d. Chemistry: CRP, ESR, AST, ALT, LDH, total bilirubin, alkaline phosphatase, total protein, albumin, sodium, potassium, chloride, carbon dioxide, calcium, blood urea nitrogen, creatinine, creatinine clearance, glucose
- e. Coagulation: Prothrombin Time (PT)/aPTT/INR, D-dimer
- f. Pregnancy Test (WOCBP) Women of Child Bearing Potential. If done prior to baseline as part of hospitalization, this does not need to be repeated.
- g. ABGs to be done prior to infusion, and 1-4 hours after each infusion
- h. Three infusions will be given on days 1, 2 and 3.
- i. All Days will be calculated from the first infusion, or Day 1.
- j. These elements will be done on Day 1, Day 2, and Day 3. Premedications, and vital signs will also be done at each infusion. Physical exams will be done daily during hospitalization and data will be pulled from those clinical notes.
- k. Monitor the use, duration, and if applicable, the dose during hospitalization
- I. Only SAEs are gathered at Day 90
- m. If use of oxygen is required at Day 90 will be documented
- n. Day 28 is the time the primary endpoint will be evaluated.
- o. Day 90 is assessing survival, SAEs, and if oxygen is still required. This may be a face time interview via the telephone.
- p. Demographics will include Date of Birth, Sex, and Race.

Confidential Page 23 of 33

^{*} The "*" signifies that the test results from standard of care testing will be used; however, they do not need to be obtained specifically for the study.

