3.3. OBJECTIVES

The Primary Objective of this study is safety of the Investigational Product, hCT-MSCs.

The primary endpoint is safety measured by:

- 1. Incidence of infusion reactions
- 2. Incidence of later reactions attributed to the investigational product Formation of new anti-PRA antibodies

The Secondary Objective of this study is to describe the potential for MSC therapy to favorably alter the course of COVID-ARDS. Endpoints are:

- 1. Time to recovery, defined as discharge from the hospital (alive) or remaining in the hospital without the need for supplemental oxygen or other COVID-related medical care.
- 2. Increase in PaO2/FiO2 ratio by 50% by Day 4 (96 hours after first infusion). PaO2/FiO2 may be calculated from an arterial blood gas or imputed from the SpO2/FiO2 table (Brown, et al. Chest 2016).
- 3. Days to hospital discharge to home
- 4. # of ventilator free days
- 5. # of days requiring O2 support
- 6. Feasibility of accrual to the randomized portion of this study

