8.3 TIME PERIOD AND FREQUENCY FOR EVENT ASSESSMENT AND FOLLOW-UP

The occurrence of an AE or SAE may come to the attention of the treating physician during patient visits or any other times the patient requires medical care. Information to be collected includes event description, time of onset, clinician's assessment of severity, relationship to investigational product (assessed only by those with the training and authority to make a diagnosis), and time of resolution/stabilization of the event. All AEs will be followed to adequate resolution.

Any condition present before the first treatment/infusion, including pre-existing conditions and pretreatment protocol AEs, will be considered medical history and will not be reported as a treatmentemergent AE unless the condition worsens during or after infusion. Any worsening (i.e., any clinically significant adverse change in frequency and/or intensity) of a preexisting condition, which is temporally associated with the use of the investigational agent, is also an AE.

Changes in the severity of an AE will be documented to allow an assessment of the duration of the event at each level of severity to be performed. AEs characterized as intermittent require documentation of onset and duration of each episode.

Patients will be followed daily while in hospital and for 7 days after administration of infusion. In addition, patients will be followed up to 90 days after administration for severe adverse events and survival. However, data analysis will be conducted at 30 days for purposes of publication and dissemination of information.

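### No adverse-event assessment is scheduled at Day 28, when a primary safety endpoint that includes non-serious late reactions is evaluated

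*Combined protocol and SAP*

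**What the plan says.** Section 3.3 lists, within the primary safety endpoint, "Incidence of later reactions attributed to the investigational product". It gives neither a time window nor a seriousness threshold. Footnote n to the schedule in Section 7 fixes the timing: "Day 28 is the time the primary endpoint will be evaluated".

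The Adverse Events Assessment row of that schedule is marked on infusion days, Day 4, Day 7 and Day 90, and is blank at Day 14 and Day 28. The Day 90 mark is narrow: "Only SAEs are gathered at Day 90". Section 6.1.2 says the same: "Follow up at 90 days will be to assess for any delayed SAEs".

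Section 8.3 describes follow-up in words: "Patients will be followed daily while in hospital and for 7 days after administration of infusion". After that, up to Day 90, it names only severe adverse events and survival. Section 6.1, by contrast, describes adverse-event monitoring from consent for as long as the patient takes part.

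A Day 28 contact does exist. Section 6.1.2 states: "Patient will have a follow-up visit at Day 28 (+/-2 days) and 90 days after Day 1 of investigational product administration".

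**The concern.** Safety is the primary objective, and one of its components is open to events of any seriousness that appear after the infusions. Once the 7-day follow-up ends, whether a non-serious event of this kind is recorded depends on the patient still being in hospital. A discharged patient comes to the Day 28 visit, but no passage requires that patient to be asked about adverse events.

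Two consequences follow. First, the late-reaction proportion may be undercounted. Second, discharge alive is part of the Phase II recovery outcome (Section 9.1.2), so the time at risk for recording a safety event can depend on an efficacy outcome. If one arm goes home sooner, it is observed for less time, and a lower late-reaction count could partly reflect that. This second consequence arises only if length of stay differs between arms.

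**Working it through.** **1. Reading the schedule.** The row was matched to the seven visit columns:

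| Row | Baseline | Infusion | Day 4 | Day 7 | Day 14 | Day 28 | Day 90 |
|---|---|---|---|---|---|---|---|
| Adverse events | | X | X | X | | | X |
| PRA | X | | | | | X | |
| Survival | | | | | | X | X |

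The PRA and survival rows fall where the text says they should, so a misaligned table is an unlikely explanation for the blank at Day 28. Section 8.3 independently narrows follow-up after the first week.

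**2. What is covered, component by component.**
- Infusion reactions: they fall on assessed days.
- New anti-HLA antibodies: PRA is drawn at baseline and Day 28.
- Serious late reactions: followed to Day 90.
- Non-serious late reactions in inpatients: daily follow-up.
- Non-serious late reactions in discharged patients: nothing scheduled from Day 8 (7 days after the first infusion on Day 1) or Day 10 (7 days after the third on Day 3) until Day 28, and no enquiry at Day 28 itself.

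**3. Indirect routes at Day 28.** Section 6.1.1 says "The treating physician will review all clinical laboratory results, and clinically significant findings will be reported as AEs", and Section 6.1.2 treats vital signs likewise. At Day 28, however, vital signs and physical examination are not marked. Every laboratory test except PRA is starred, which means "test results from standard of care testing will be used; however, they do not need to be obtained specifically for the study". Concomitant medications are marked without a star, so new treatment would be recorded, but the event behind it need not be.

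**4. The plan's own detection figures.** Section 9.1.1 gives the chance of seeing at least one reaction in 10 patients. With 1 - (1 - p)^10:
- p = 0.10: 0.6513 (stated 0.65)
- p = 0.25: 0.9437 (stated 0.94)
- p = 0.33: 0.9818 (stated 0.98)

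These reproduce and are not in dispute. They presuppose that every reaction is recorded. If only a share c were recorded, p becomes c × p. At p = 0.10, c = 0.75, 0.50 and 0.25 give 0.54, 0.40 and 0.22. The documents give no value for c, so this shows direction only.

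**5. Illustration of unequal observation in Phase II.** Inputs from Section 9.1.2: 30% placebo recovery by Day 28, 20 patients per arm, and the hazard ratio of 2.0 used there as a power example. Assumptions added here: all recovery is discharge, and nobody dies.

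- Placebo hazard: h = -ln(0.7)/28 = 0.01274 per day; at hazard ratio 2.0 it is 0.02548.
- Recovered by Day 28: 0.30 × 20 = 6.0 on placebo; (1 - 0.7²) × 20 = 0.51 × 20 = 10.2 on hCT-MSC.
- Mean days outside scheduled follow-up, Day 10 to Day 28, constant hazard: 18 - [exp(-10h) - exp(-28h)]/h.
- If all recoveries come before Day 10: proportion recovered × 18. This is an extreme case for contrast.

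| Case | Placebo | hCT-MSC, HR 2.0 | hCT-MSC, HR 1.0 |
|---|---|---|---|
| From Day 10, constant hazard | 3.84 | 6.81 | 3.84 |
| From Day 10, all recoveries earlier | 5.40 | 9.18 | 5.40 |
| From Day 8 (20 days), constant hazard | 4.06 | 7.22 | 4.06 |
| From Day 8, all recoveries earlier | 6.0 | 10.2 | 6.0 |

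**The case against.** The strongest reply is that the table lists minimum marks and is not the whole collection plan. Section 6.1 gives a general rule of monitoring throughout participation; only Day 90 is expressly limited to serious events; the Day 28 visit sits under a safety heading; and Section 8.3 lets events come to attention at any visit. The required Day 28 medication review could also expose a treated reaction, and Section 6.1.2 calls for a complete examination at end of treatment or termination. On this reading the fault is inconsistent wording, not excluded data. Much of that stands: some late non-serious events would be recorded. But these routes are passive or indirect, the termination examination has no date, and Section 8.3 itself narrows later follow-up.

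The gap may also be smaller than *non-serious* suggests. Section 8.3 speaks of severe events, and the abbreviation list expands SAE that way, so severe but non-serious events may be followed to Day 90. That ambiguity is real and leaves mild and moderate events as the certain gap.

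Footnote n may mean only that analysis starts at Day 28. Even so, a component evaluated then needs data up to then, or a stated earlier cut-off.

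The illustration counts days, not reactions. It ignores deaths, although the synopsis cites 30-60% ARDS mortality and Section 3.6 reports Phase 1 deaths on days 7 and 27. It also treats recovery in hospital as discharge. These criticisms are fair, and the conclusion does not rest on it. Nothing in the documents gives a rate for late non-serious reactions, so materiality is not shown either way.

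**Conclusion.** The concern holds in its narrow form. For one component of the primary safety endpoint, non-serious product-attributed reactions in discharged patients between about Day 8-10 and Day 28 have no scheduled enquiry, so they may be missed. Sections 6.1, 7 and 8.3 disagree on what is collected and until when. Infusion reactions, PRA and serious events are not affected. The safety analysis is descriptive (Section 9.4), so neither type I error nor power is involved.

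The number of reactions lost cannot be derived. Under the stated assumptions, a true hazard ratio of 2.0 would leave the hCT-MSC arm with about 3 more days per patient outside scheduled follow-up from Day 10 (6.81 - 3.84 = 2.97) under a constant hazard, or 3.78 more (9.18 - 5.40) if all recoveries came before Day 10. With equal recovery the difference is zero. A hazard ratio of 2.0 is the plan's power example, not an expected effect. The point should be corrected because the remedy is small and the endpoint is primary, not because a large bias has been shown.

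**What to change.** Mark Adverse Events Assessment at the existing Day 28 visit, with an enquiry reaching back to the last assessment. Reconcile Sections 6.1, 7 and 8.3 so that they state one collection period for all adverse events and one for serious events, and say whether *severe* in Section 8.3 means serious.

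Two minor wording changes belong with this:
- Section 9.4 tabulates product-related reactions other than infusion reactions only if they are unexpected, a filter the endpoint lacks. Remove it, tabulate all product-attributed reactions by arm and grade, and name new anti-HLA antibodies at Day 28.
- Section 9.3 analyses all Phase II patients as assigned and defines no safety set. Analyse safety in patients who received any part of an infusion, by product received, and keep intention-to-treat for efficacy.

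The cost is one mark at a visit that already takes place, short edits to Sections 6.1, 8.3, 9.3 and 9.4, and slightly more adverse-event data to process. No visit, procedure or patient is added. Section 3.6 reports Phase 1 as fully enrolled, so the added assessment would serve Phase II.
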